A randomized controlled approach will explore the effects music has on stress and anxiety levels and academic performance among undergraduate nursing students. The study will be conducted with nursing students in the first semester of the undergraduate BSN program at UT Health Science Center at San Antonio. The study will consist of Phase 1 (pilot) and Phase 2 (larger dissertation study). Phase 1 will be the pilot study conducted in Spring 2022. The total population of the cohort typically consists of \approx 108 students. Approximately half-way through the semester, the students are required to sign-up for a skills competency recording. The students select the best date and time for their schedule. Students sign-up electronically into a group consisting of up to 10 students. Typically, there are 30 min time slots available for sign-up. For Phase 1, the pilot study will use a cluster randomization procedure to randomly assign two of the sign-up groups. The two groups will be 1) the music intervention group (n=up to 10 participants), and 2.) the non-music control group (n= up to 10 participants). An online randomizer will be used to create the groups. Students assigned to these groups will be allowed to remove themselves. The academic performance of these students will be recorded for the study.

Phase 2 of the study will be informed from the findings of Phase 1, the pilot study. It is anticipated there will be no intended changes in the methodology or randomization procedures from Phase 1 to Phase 2. The only difference would be in Phase 2 the total population in the Summer 2022 cohort (\approx 108) will be randomized into approximately 6 slots per half hour. Any changes to be made for Phase 2 will be immediately communicated to the IRB for approval prior to implementation.

The following procedures will be used for Phase 1 and Phase 2:

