The study will be conducted at the UT Health Science Center - San Antonio's Center for Simulation Innovation (CSI). Two classrooms will be reserved in the CSI area at the School of Nursing. Students will be divided into the recording time slots consisting of no more than 10 students at a time. The students receiving the music intervention will be assigned an iPad (only used to sync smartwatch), a hard copy of State Trait Anxiety Inventory (STAI) survey forms Y-1 and Y-2, a demographic data form, pencil, and smart watch. Students will be advised to sit quietly, with desks spread out, in the reserved room. The participants will be asked to complete the STAI survey forms prior to music listening. Students will be advised to wear the watch, and watches will be previously logged in and synced by researcher to measure heart rate and blood pressure. Vital sign sheet will be completed by researcher using the data from the iPad. Fifteen minutes of classical music will be played overhead in the classroom. The students will be instructed not to use other electronic devices such as ear buds or phones during this time. The STAI survey Y-1 will be completed again post-intervention, and heart rate and blood pressure re-assessed. Students will then proceed to perform the skills competency assessment. Vitals and STAI survey Y-1 will then be reassessed post-skills competency and academic performance (pass/fail) will be measured.

The students who will not be receiving the music intervention (control group) will be seated in a second reserved classroom and will be repeating the same process as the music intervention group except without music, instead they will be sitting quietly for 15 minutes waiting to record their skills competency. The students will also be instructed not to use other electronic devices such as ear buds or phones during this time. For any students who have been randomly assigned to either group, and refuse to be in the study, they

will be allowed to leave. Only the academic performance will be measured on these students that refuse to be assigned to a group.

Data Analysis Plan:

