A priori power analysis was conducted using G*Power 3.1.9 to determine the minimum sample size required to find statistical significance using a 3 (group) x 4 (time) repeated measures analysis of variance (i.e., a mixed-model ANOVA). With a desired level of power set at .80, an alpha (α) level at .05, and a moderate effect size of .25 (f), it was determined that a minimum of 30 total participants would be required to ensure adequate power (Cohen, 1988).

Mean heart rate, mean blood pressure, mean scores on STAI, and academic performance score (Pass/Fail) will be calculated for all groups. Demographic data will be analyzed in terms of frequencies and comparisons between groups. For RQ1: Pearson's correlation will examine the relationship between the music intervention on stress, anxiety, and academic performance. For RQ2: To measure anxiety, STAI mean scores will be analyzed. For RQ3: To measure stress levels, the mean heart rate and mean blood pressure will be analyzed. For RQ4: To assess academic performance, Pass/fail scores will be looked at. MANOVA will be considered for data analysis since there is one independent variable (music intervention) and multiple dependent variables. If any variables are not correlated, running a repeated-measures ANOVA to detect any overall differences between any related means would be considered. A paired samples t-tests could also be used for pre-and post-comparisons of vital signs. Using a Chi-Square test can also be beneficial in determining any differences in demographics and anxiety and/or stress. Alpha will be set at 0.05 for the study.

Item 7 Risks Section:

Complete the following table to describe the risks of all **research procedures** listed in Step 2, Institutional Form (items 28-34). *Do not list risks of Routine care procedures here.*

N/A, Risks are described in the informed consent document – do not complete this table.

Research procedures	Risks

example:
 
 • History and physical • Questionnaire • Laboratory tests 	
List the reasonably expected risks under the following categories as appropriate:

Add or delete rows as needed	
Vitals Signs obtained via SmartWatch	
Serious and likely;
 
 ○ None 
Serious and less likely;
 
 ○ None
Heart Rate Blood Pressure	
Demographic data form, paper and pencil	
Serious and likely;
 
 ○ None

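### Students may leave after random assignment with only pass/fail kept; the plan does not tie that result to the assigned arm, and it specifies no analysis with baseline STAI or vitals as a covariate

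*Combined protocol and SAP*

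**What the plan says.** **Leaving after assignment.** Item 6, Step-by-Step Methods, says of the Phase 1 groups: "Students assigned to these groups will be allowed to remove themselves". The next sentence is "The academic performance of these students will be recorded for the study", without saying in which arm. The procedures common to Phases 1 and 2 return to the matter. They begin with "For any students who have been randomly assigned to either group, and refuse to be in the study", let these students go, and end with "Only the academic performance will be measured on these students that refuse to be assigned to a group". The same students are thus described both as assigned and as refusing assignment.

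**Baseline.** The procedures state: "The participants will be asked to complete the STAI survey forms prior to music listening". Heart rate and blood pressure are described as re-assessed after the 15 minutes, which implies a first reading. The control room follows by "repeating the same process as the music intervention group except without music", so both arms have baseline values. STAI Y-1 and vitals are taken a third time after the skills assessment.

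**Analysis.** The Data Analysis Plan says that the "academic performance score (Pass/Fail) will be calculated for all groups", without defining the groups or placing refusers in one. On research question 4 it says only: "For RQ4: To assess academic performance, Pass/fail scores will be looked at". It names Pearson's correlation, MANOVA, repeated-measures ANOVA, paired t-tests and chi-square, several of them as possibilities. The sample size rests on a 3 (group) by 4 (time) mixed-model ANOVA. It states no baseline covariate, analysis population or rule for missing data.

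**The concern.** Two gaps meet here.

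First, refusers contribute no STAI or vitals, so those outcomes can be compared only among students who stay. If leaving differs by arm and is related to anxiety, the stayers in the two arms are no longer fully comparable. Pass/fail need not suffer from this, because it is recorded for refusers too. But the plan leaves open whether a refuser counts in the assigned arm, in a separate group or nowhere, so that choice could be made after the results are seen.

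Second, the plan collects a baseline for each continuous outcome but does not commit to the comparison that uses it most efficiently. In a cohort of about 108 students, less whoever leaves, that loss of precision matters.

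**Working it through.** **1. The plan's own figure.** For the 3 by 4 interaction, with f = .25, N = 30 and alpha .05, and assuming a correlation of .5 between occasions and sphericity (neither is stated): λ = f²·N·m/(1−ρ) = .0625 × 30 × 4 / .5 = 15, on 6 and 81 degrees of freedom. Power is .809; at N = 27 it is .754. The stated minimum of 30 is therefore reproduced as a group-by-time test, and that test does use baseline as one of its occasions.

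**2. What that test does with baseline.** In a numerical check with two groups and two occasions, the interaction F and the squared t for change from baseline were both 3.589. It is a change-score comparison, not a covariate adjustment.

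**3. Precision.** Assumptions: the Phase 2 cohort of about 108 is split 54 and 54; 10% and 20% leave, so 54 × .9 ≈ 49 and 54 × .8 ≈ 43 stay; the effect is 0.5 SD; the baseline-to-post correlation is ρ = .6; students are independent. Relative variances are 1 (post only), 2(1−ρ) = .8 (change) and 1−ρ² = .64 (ANCOVA). The noncentrality is 0.5/√[v(1/49 + 1/43)].

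| Analysis | v | Noncentrality | Power |
|---|---|---|---|
| Post score only | 1 | 2.39 | 66% |
| Change score | .80 | 2.68 | 75% |
| ANCOVA | .64 | 2.99 | 84% |

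For ρ from .5 to .7, ANCOVA power runs from 78% to 91%. For a 0.3 SD effect at ρ = .6 the three figures are 30%, 36% and 43%.

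If Phase 2 keeps sign-up groups as clusters (assumed: 6 clusters of 9 per arm, intracluster correlation .05), the design effect is 1 + 8 × .05 = 1.4. With 12 − 2 = 10 degrees of freedom, the 0.5 SD powers fall to about 45%, 53% and 63%. The order is unchanged.

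**4. Bias in STAI and vitals among stayers.** Suppose a student leaves when a normal propensity, correlated r = .5 with baseline, exceeds its (1−p) quantile z. The stayers' baseline mean is then −r·φ(z)/(1−p): −0.098 SD at p = 10%, −0.175 at 20% and −0.248 at 30%. The post-score bias is ρ times the difference between arms; the change-score bias is −(1−ρ) times it. Type I error is from simulation with no true effect, 54 per arm and independent students.

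| Leaving by arm | Post score (error) | Change score (error) | ANCOVA (error) |
|---|---|---|---|
| 20% vs 20% | 0.00 SD (5%) | 0.00 (5%) | 0.00 (5%) |
| 10% vs 20% | −0.05 (5%) | +0.03 (5%) | 0.00 (5%) |
| 10% vs 30% | −0.09 (7%) | +0.06 (6%) | 0.00 (5%) |

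The ANCOVA zeros follow from the set-up: leaving is linked to outcome only through baseline. With a residual correlation of .3 between leaving and the post score, at 10% vs 30% the ANCOVA bias is 0.07 SD and the change-score bias 0.00.

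**5. Pass/fail.** Assume that both arms truly pass at 85% and refusers at 70%. Stayers pass at (.85 − .70p)/(1−p). At p = .10 this is .78/.90 = 86.7%; at p = .30 it is .64/.70 = 91.4%. A stayers-only comparison shows a gap of 4.8 points with no true difference, and its simulated type I error is about 10%. By assigned arm it is 85% vs 85%, with error about 5%.

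**The case against.** **Baseline is not ignored.** A reader might infer that none of the named methods uses it. The documents do not support that. The group-by-time ANOVA behind the sample size, and the optional repeated-measures ANOVA if run with group as a factor, use baseline as a repeated measure. In simulation that test (2 groups, 3 occasions) also holds its error rate well: 5.0% at 10% vs 20% leaving and 5.7% at 10% vs 30%, against 4.9% and 4.8% for ANCOVA. This stands. What remains is that no covariate adjustment is specified and that the change-score form has less power.

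**Adjustment does not cure refusal.** A reader might also infer that the results will be biased by refusal and that ANCOVA removes the bias. Neither follows. The documents give no refusal rate and no reason for it to differ by arm. ANCOVA removes only the part that runs through baseline, and with an unmeasured cause of leaving it can do worse than a change score. This also stands, so precision is the main argument for it.

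**Clustering.** The error and power figures assume independent students, while Item 6 describes cluster randomisation in Phase 1 and anticipates no change in procedure for Phase 2. With 6 assumed clusters of 9 per arm, student-level ANCOVA that ignores clusters rejects in about 7%, 9% and 14% of null trials at intracluster correlations of .02, .05 and .10. This stands: the adjusted analysis must respect the unit of randomisation.

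**Pass/fail is only a wording gap.** Assigned arm can probably be recovered from the sign-up group and the randomiser. That is a fair inference, but the plan does not say so, and the conflicting description of refusers leaves the choice open.

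**Knowledge of the condition.** A reader might infer that students learn which room gets music before deciding to leave. The visible text does not say, and the consent pages are not shown.

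**Conclusion.** The point holds as two specification gaps, worth closing but not fatal to the study.

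On pass/fail, the text is inconsistent about refusers and silent on their arm. The possible distortion ranges from nothing, if leaving is alike in both arms, to about 5 percentage points under the assumed 10% vs 30% leaving and a 70% pass rate in refusers. Analysis by assigned arm removes it.

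On STAI and vitals, the plan specifies no baseline-covariate analysis. Under the stated assumptions, adding one raises power for a 0.5 SD effect from 66% (post score) or 75% (change score) to 84%, with lower values for all three under clustering. Bias from refusal remains a possibility and has not been shown. At 10% vs 20% leaving it is about 0.05 SD on the unadjusted post score, and adjustment cannot be relied on to remove it. Leaving rates, correlations, effect sizes and pass rates are all assumptions.

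**What to change.** 1. State that post-intervention and post-skills STAI, heart rate and blood pressure will be compared between arms with the pre-music value as covariate (ANCOVA or equivalent), in a form that respects the unit of randomisation. Label these as results in students who stayed.
2. Reconcile the two descriptions of refusers in Item 6. Keep each refuser's assigned arm on record, analyse research question 4 by assigned arm in all assigned students, and report the number leaving in each arm.
3. Ask the investigator whether students know their condition when they decide to leave. This is a query only.

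**Cost.** A few sentences in the analysis plan, with no new data and no added students.

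**Downsides.** If 10% to 30% of the music arm leave, the as-assigned pass/fail contrast keeps only about 70% to 90% of the effect. If leaving has an unmeasured cause, the adjusted result can be more biased than a change score (0.07 vs 0.00 SD at 10% vs 30%), so showing the change-score result beside it is sensible.

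**Limits.** The change does not supply refusers' missing STAI and vitals. Nor does it separate arm from sign-up slot in Phase 1, where each arm is a single group.

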Describe past experimental and/or clinical findings leading to the formulation of your study. For research involving unapproved drugs, describe animal and human studies. For research that involves approved drugs or devices, describe the FDA approved	Nursing students experience higher levels of stress than students in any other health science academic programs (Kinchen & Loerzel, 2019). Since most nursing students are not able to avoid these stressors, students must be able to cope with them. If students are not able to manage their stress, it can affect their performance, health, attitude, and role satisfaction as a nurse (Rafati et al., 2017). The levels of stress may vary during students' educational training, depending on their ability to adopt various strategies or coping with stress, and other factors. Even though numerous studies have been published regarding stress and anxiety among nursing students, few studies are found addressing the benefits of music utilized as an intervention to decrease emotional stress.

uses of this drug/device in relation to your protocol.
	

Item 4 Purpose and rationale Insert purpose, objectives and research questions/hypotheses here. If you cut and paste from another document, make sure the excerpted material answers the question
	
Music is an immensely powerful emotional tool that can be used as a coping mechanism for stress, but there is truly little existing research about its use by students. This study aims to explore the effects of music intervention on the stress and anxiety levels among nursing students in their first semester of undergraduate studies. Increased awareness of their own strategies used, as well as the willingness to use holistic methods such as music, can offer a non-pharmacological and inexpensive intervention to many institutions.
 
Research Questions:
 
 1. Is there a relationship between listening to music and stress, anxiety, and academic performance among new undergraduate nursing students? 2. Does listening to music help in decreasing anxiety among new undergraduate nursing students who are anticipating a skills assessment? 3. Does listening to music help in decreasing stress among new undergraduate nursing students who are anticipating a skills assessment? 4. Does listening to music help to improve academic performance among new undergraduate nursing students?

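### RQ1's Pearson correlation with arm is an unadjusted two-group test of the outcomes that RQ2 to RQ4 already cover, and no rule says which analysis answers the question

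*Combined protocol and SAP*

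**What the plan says.** Item 4 opens its research questions with "Is there a relationship between listening to music and stress, anxiety, and academic performance among new undergraduate nursing students". RQ2, RQ3 and RQ4 then ask in turn whether music lowers anxiety, lowers stress and improves academic performance. These are the same three music-outcome pairs.

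The Data Analysis Plan in Item 6 assigns methods as follows:

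- RQ1: Pearson's "correlation will examine the relationship between the music intervention on stress, anxiety, and academic performance".
- RQ2: "To measure anxiety, STAI mean scores will be analyzed".
- RQ3: "To measure stress levels, the mean heart rate and mean blood pressure will be analyzed".
- RQ4: "To assess academic performance, Pass/fail scores will be looked at".

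Only RQ1 has a committed test. The other methods are listed as possibilities: "MANOVA will be considered for data analysis since there is one independent variable (music intervention) and multiple dependent variables"; if variables are not correlated, "running a repeated-measures ANOVA to detect any overall differences between any related means would be considered"; and "A paired samples t-tests could also be used for pre-and post-comparisons of vital signs". Chi-square is mentioned for demographics and for anxiety or stress, not for pass/fail. Alpha is 0.05 for the study, with no allocation across tests. The sample size is justified on a group-by-time repeated-measures ANOVA, not on a correlation.

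Under the step-by-step methods of Item 6, STAI Y-1 and vital signs are taken three times: before the 15-minute period, after it, and after the skills assessment. A baseline value is therefore collected for every continuous outcome.

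**The concern.** A correlation describes how two measured quantities vary together. Here one of the two is the randomised arm, so the correlation is a treatment comparison in another form. RQ1 is then not a separate question, and its test is a second route to the answers for RQ2 to RQ4.

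Two things are at stake. First, the only committed test suits the data poorly: as written it leaves the collected baseline unused, does not say which of the two later readings it applies to, and reports its result on a scale that no reader can translate into an effect. Second, for anxiety and stress the same data could show no relationship with music under RQ1 and a reduction under RQ2 or RQ3. Nothing in the plan says which result would stand.

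**Working it through.** **Inputs from the documents.** Two arms (Item 2). Three measurement occasions (Item 6). Phase 1 has up to 10 students per arm, so at most 20. Phase 2 has about 108. The planned minimum is 30, with alpha .05, power .80 and f = .25.

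**Inputs assumed.** The documents give no SDs or within-student correlations. I take an effect of 0.5 SD at both later occasions, an equal correlation rho of .3, .5 or .7 between occasions, and independent students.

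**Step 1: what the plan's N rests on.** For the group-by-time interaction with k = 3 groups and m = 4 times, lambda = f²·N·m/(1 − rho), df1 = (k − 1)(m − 1) and df2 = (N − k)(m − 1). With N = 30 and rho = .5, lambda = .0625 × 30 × 4/.5 = 15, with 6 and 81 degrees of freedom. Power is .809, and 30 is the smallest N that reaches .80. The stated 30 is thus reproduced by an arm-by-time test at rho = .5, not by a correlation.

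**Step 2: what the Pearson test is.** With arm coded 0/1, t = r·√(N − 2)/√(1 − r²) is the pooled two-sample t statistic on N − 2 degrees of freedom. In a numerical example with N = 30, both p-values were .93672. For pass/fail, r is phi, and N·r² is the uncorrected chi-square statistic (.6818 by both routes in an example).

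**Step 3: anxiety and stress.** I simulated 20,000 trials per setting and scored each test at .05. Pearson was applied to the reading after the 15-minute period. The table gives the share of trials in which the two tests reach opposite verdicts under the assumed effect.

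| N | rho | Pearson vs arm-by-time | Pearson vs MANOVA over the three occasions |
|---|---|---|---|
| 30 | .3 | 28% | 21% |
| 30 | .5 | 31% | 22% |
| 30 | .7 | 40% | 28% |
| 108 | .3 | 38% | 20% |
| 108 | .5 | 33% | 21% |
| 108 | .7 | 28% | 25% |

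Repeat runs move these by about a point, giving ranges of 27-40% and 19-28%. At N = 20, disagreement with the arm-by-time test is 22%, 25% and 32%. If Pearson is applied to change from baseline instead, disagreement with the arm-by-time test falls to about 13-17% at N = 30 and 6-18% at N = 108.

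With no effect, at least one of post-score Pearson and arm-by-time is significant in about 9% of trials (8.5% to 9.8% across settings). With MANOVA or with change scores the figure is about 8%. If the two tests were independent it would be 1 − .95² = 9.75%.

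**Step 4: pass/fail.** Exact enumeration at N = 20, 30 and 108, with assumed pass rates of .8/.8, .9/.9 and .7/.9, gave no disagreement between Pearson and the uncorrected chi-square.

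**Step 5: what ignoring the baseline costs.** At N = 108 and d = 0.5, the noncentrality is 0.5 × √(108/4) = 2.60 and power is 73%. Adjusting for a baseline with rho = .5 divides d by √(1 − .25), giving 0.577. The noncentrality becomes 0.577 × √27 = 3.00 and power 84%.

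**The case against.** A reader might infer that every music-outcome question gets two planned tests that often contradict each other. The documents do not support that. RQ2 to RQ4 commit to no test at all, and MANOVA, repeated-measures ANOVA and paired t-tests are only options. For academic performance there is no conflict to find, because Pearson and the uncorrected chi-square agree throughout. Pearson is also the only test that the plan ties to pass/fail, so deleting it without a replacement would leave RQ4 with none.

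The disagreement rates depend on choices that the plan does not make. It does not say whether post scores or changes are correlated, and MANOVA is listed ahead of repeated-measures ANOVA; either alternative gives a lower rate. A single-occasion contrast and an arm-by-time interaction also estimate different things, so different verdicts are not a logical contradiction, particularly at about 26% power for N = 30.

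Nor should a reader take 9% as this trial's error rate. It arises only if a claim is made from whichever test is significant, which the plan allows but does not propose. The simulation also treats students as independent, whereas Phase 1 randomises sign-up groups.

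The plan does calculate group means for STAI, heart rate and blood pressure, so differences in natural units could be derived, although no interval is specified.

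One could read RQ1 as asking for correlations among the outcomes. Its wording, in both Item 4 and Item 6, puts music on one side of the relationship.

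All of this limits the size of the point. It leaves standing that the one committed test is an unadjusted arm comparison under another name, with no rule relating it to whatever is done for RQ2 and RQ3.

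**Conclusion.** The point holds in limited form. The RQ1 correlation duplicates the arm comparisons of RQ2 to RQ4, and as stated it uses no baseline and names no occasion. That equivalence is algebra and needs no assumption.

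For anxiety and stress, the lack of a choosing rule matters: opposite verdicts in roughly 6% to 40% of trials at N = 30 or 108, depending on the score correlated and the comparator, with the upper part of that range (27-40%) for post scores against the arm-by-time test. These rates are illustrative and rest on the assumed 0.5 SD effect, rho of .3 to .7 and independence between students. For pass/fail the test is redundant only. The change should be made, but it is an improvement to the analysis plan rather than a flaw in the design.

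**What to change.** - Remove the Pearson correlation with arm as a test, and state that RQ1 is answered by the arm differences reported for RQ2, RQ3 and RQ4.
- For STAI Y-1, heart rate and blood pressure, name one baseline-adjusted arm comparison at a stated occasion, reported in points, beats per minute or mmHg with a 95% confidence interval.
- For pass/fail, name one two-group comparison of proportions with a 95% confidence interval, so that RQ4 has a test.
- Make the chosen analyses respect randomisation by sign-up group. In Phase 1 each arm is a single sign-up group, so group and music effects cannot be separated there and the results should be treated as descriptive.
- Label any correlations among anxiety, heart rate, blood pressure and passing as exploratory, adjusted for arm, and not as evidence about music.

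The cost is a redundant set of p-values and a few sentences of analysis-plan text. No measurement, visit or recruitment target changes.

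### The pass/fail outcome is given only a Pearson correlation and RQ4 names no comparison, so the plan yields no pass-rate difference or confidence interval and takes no account of the sign-up groups.

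*Combined protocol and SAP*

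**What the plan says.** Item 4 poses RQ4 as a comparative question: "Does listening to music help to improve academic performance among new undergraduate nursing students". Item 6, Step-by-Step Methods, records academic performance once, as pass or fail, after the skills assessment.

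Item 6, Data Analysis Plan, deals with this outcome in four places:

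- A pass/fail score is to be calculated for each group, next to mean heart rate, blood pressure and STAI.
- RQ1 uses Pearson's method: "correlation will examine the relationship between the music intervention on stress, anxiety, and academic performance".
- RQ4: "Pass/fail scores will be looked at". No test, effect measure or interval follows.
- A joint analysis is possible: "MANOVA will be considered for data analysis since there is one independent variable (music intervention) and multiple dependent variables". The dependent variables are not listed.

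Chi-square is mentioned for demographics and for anxiety or stress, not for pass/fail. On error rate: "Alpha will be set at 0.05 for the study". Phase 1 allocates by cluster, with one sign-up group of up to 10 students per arm. Phase 2 takes the whole cohort of about 108 and anticipates no change in randomization procedure.

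**The concern.** RQ4 needs the difference in pass rates between the arms and a statement of its precision. Followed as written, the plan gives a unitless coefficient under RQ1 and an inspection of scores under RQ4. A reader of the results could not tell whether a null finding rules out a worthwhile change or merely reflects few failures and a small sample.

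Two further problems come with the chosen method. A student-level correlation treats students as independent, although they are allocated and exposed in groups. And the coefficient does not exist when nobody fails, which could happen in the pilot. If MANOVA were taken up with pass/fail among its outcomes, a variable that is not normal, and that has zero variance in an all-pass arm, would enter a method that assumes normal outcomes with equal covariance matrices. A significant joint test would also not say which outcome moved.

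**Working it through.** **Inputs from the documents.** Alpha 0.05 (taken as two-sided, since the plan does not say); up to 10 per arm in Phase 1; about 108 students in Phase 2. **Assumptions.** 54 per arm in Phase 2, because no allocation ratio is given; pass rates of 80%, 90% and 95%, because none is given.

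**1. The plan's own figure.** The sample size is for a 3 x 4 mixed ANOVA with f = 0.25 and power 0.80. For the within-between interaction, with correlation 0.5 between repeated measures and no sphericity correction (neither is stated), λ = f²·N·m/(1-ρ) = 0.0625 × 30 × 4 / 0.5 = 15 on (3-1)(4-1) = 6 and (30-3)(4-1) = 81 df. Power is 0.809, so the stated minimum of 30 reproduces. It concerns a continuous outcome and contains no pass rate, so it gives RQ4 no support.

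**2. What Pearson's r does here.** Take 50/54 v 44/54 passing.
- r = (50×10 - 4×44)/√(54×54×94×14) = 324/1958.9 = 0.165.
- N·r² = 2.954, which equals the uncorrected chi-square, 2.954.
- p = 0.087 (Pearson t) v 0.086 (chi-square).

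Exact enumeration at 54 per arm gives null rejection rates of 0.051, 0.050 and 0.045 at pass rates of 80%, 90% and 95%. For independent students, the test is sound.

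**3. What it leaves out.** Take 51/54 v 46/54, where r = 0.153. The difference is 94.4% - 85.2% = 9.3 points. The Wilson limits are 84.9 to 98.1% and 73.4 to 92.3%, and Newcombe's method gives:
- lower: 0.0926 - √[(0.9444-0.8489)² + (0.9230-0.8519)²] = -0.026
- upper: 0.0926 + √[(0.9809-0.9444)² + (0.8519-0.7340)²] = 0.216

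The interval is -2.6 to +21.6 points. For 10/10 v 10/10, r is undefined, but the same method gives 0 (-27.8 to +27.8).

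**4. Chance that everyone passes.**

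| Assumed pass rate | N = 20 (p^20) | N = 108 (p^108) |
|---|---|---|
| 80% | 1% | negligible |
| 90% | 12% | 0.001% |
| 95% | 36% | 0.4% |

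**5. Allocation by group.** Assume, for illustration, 5 slots of 10 per arm, 90% passing and an intraclass correlation of 0.05. The design effect is 1 + 9×0.05 = 1.45. In simulation, an unadjusted chi-square rejects a true null about 10% of the time, not 5%.

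**6. The conditional MANOVA case.** Assume music shifts STAI only, by d = 0.5 at one time point, with N = 108, r = 0.3 among STAI, heart rate and blood pressure, and pass/fail uncorrelated with them and treated as normal. For two groups, λ = (N/4)·D².
- STAI alone: D² = 0.25, λ = 6.75 on 1 and 106 df; power 73%.
- Three outcomes: D² = 0.25 × 1.3/(0.7×1.6) = 0.290, λ = 7.83 on 3 and 104 df; power 63%.
- Pass/fail added: λ = 7.83 on 4 and 103 df; power 57%.

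Of the 16 points lost, about 5 come from pass/fail. If all three continuous outcomes shift by 0.5 in the same direction, D² = 3×0.25/1.6 = 0.469, λ = 12.66 and three-outcome power is 85%, above STAI alone.

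**The case against.** The strongest reply is that little is lost. Pearson's r on two binary variables is phi, its test is in effect the chi-square, and the plan already calculates pass/fail for each group, so anyone could derive the difference and its interval afterwards. RQ1 asks about a relationship, which a correlation does address. This stands against three stronger readings that a reader might infer.

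- **That the plan cannot show whether music changes the pass rate.** It can detect a difference, through the RQ1 test. The gap is the unspecified estimate and interval, and the disregard of grouping.
- **That pass/fail is put through MANOVA.** MANOVA is only to be considered, and its outcomes are not listed. Including pass/fail is a natural reading, since it appears alongside the other measures just before, but the text does not state it.
- **That the plan weakens its own anxiety test.** RQ2 commits to no test, only to analysing STAI means. A loss needs MANOVA to be chosen, pass/fail to be included and the joint result to replace a STAI analysis. Even then the loss is modest and can reverse.

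The undefined coefficient is also a pilot problem: at N=108 it can be ignored for pass rates of 95% or lower, and one all-pass arm alone does not cause it.

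The reply does not remove the main point. That a difference could be derived does not make it planned. RQ4 names no comparison, Pearson is assigned to RQ1, and group summaries are not a between-arm estimate with an interval.

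**Conclusion.** The point holds as a change that should be made. One of four research questions has no stated comparison, and the one inferential method given to its outcome returns neither a pass-rate difference nor an interval and treats grouped students as independent. This follows from the text and needs no assumption.

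The sizes do rest on assumptions. The all-pass chances (1%, 12%, 36% at 20 students; 0.4% or less at 108) depend on assumed pass rates of 80% to 95% and on independent students. The 10% error rate depends on an assumed intraclass correlation and slot layout. It is relevant to Phase 2 if allocation is again by sign-up group, which is the natural reading of an unchanged randomization procedure. The fall from 73% to 57% power applies only if music moves STAI alone and the joint test stands in for RQ2. It supports separate models but is not a demonstrated loss in this trial.

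**What to change.** In Item 6, Data Analysis Plan:

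- **RQ4.** Report the pass proportion by assigned arm and the risk difference with a 95% CI. State whether students who decline after assignment, whose pass/fail result is still recorded, count in their assigned arm.
- **Phase 2.** Use an analysis that allows for session, for example a session-level or cluster-robust comparison. A student-level exact test would ignore the grouping.
- **Phase 1.** With one sign-up group per arm, no student-level test can separate music from group. Report the estimate descriptively with a Newcombe interval, noting that it assumes independent students.
- **RQ1.** Replace r with between-arm differences and 95% CIs for each outcome.
- **MANOVA.** If it is kept, list its outcomes, leave pass/fail out, and do not let the joint test answer RQ2 or RQ3. Analyse STAI Y-1, heart rate and blood pressure each in its own model.

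The cost is analysis-plan wording, with no new data. Intervals may be wider once session is allowed for.
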